6.2 Primary Objective #2: Efficacy

An OPC of 88% was chosen to evaluate the primary efficacy objective metric of implant testing success defined as successfully terminating one or more induced ventricular fibrillation episodes (see CIP sections 8.5.7 and 12.5.2 for more details). Each subject who completes the defibrillation protocol will be counted as a success or failure; it is assumed the true success rate is 93.5%. The required sample size to evaluate this objective using the lower confidence bound of a two-sided exact binomial 95% confidence interval and OPC of 88% with 90% power is 292 subjects completing the defibrillation protocol. This was calculated using the statistical software package PASS 2008; see the screenshot and output below from PASS.

Figure 3: Sample Size Estimation for Primary Efficacy Objective Using PASS 2008

Power Analysis of One Proportion

**Numeric Results for testing H0: P = P0 versus H1: P > P0. N = 100000.
Test Statistic: Exact Test**

		Proportion Given H0 (P0)	Proportion Given H1 (P1)	Target Alpha	Actual Alpha	Beta	Reject H0 If R>=This
Power	N	0.8800	0.9350	0.0250	0.0243	0.0981	268

Report Definitions

- Power is the probability of rejecting a false null hypothesis. It should be close to one.
- N is the size of the sample drawn from the population. To conserve resources, it should be small.
- Alpha is the probability of rejecting a true null hypothesis. It should be small.
- Beta is the probability of accepting a false null hypothesis. It should be small.
- P0 is the value of the population proportion under the null hypothesis.
- P1 is the value of the population proportion under the alternative hypothesis.

Summary Statements

A sample size of 292 from a population of 100000 achieves 90% power to detect a difference (P1-P0) of 0.0550 using a one-sided binomial test. The target significance level is 0.0250. The actual significance level achieved by this test is 0.0243. These results assume that the population proportion under the null hypothesis is 0.8800.

7. Statistical Methods

The CIP version 1 dated July 02, 2019 is the only version as of the approval date of this document. Should there be a CIP update, the impacts of it on the integrity of the study will be evaluated; if such impacts are confirmed, the data collected before and after the amendment will be analyzed statistically per ISO 14155:2020 to assess the effect of the amendment on the safety and efficacy analysis.

7.1 Study Subjects

7.1.1 Disposition of Subjects

This is a single-arm study. After subjects sign the informed consent form, they are enrolled in the study. Screening logs are not used in this study as historically they have typically been found to have poor compliance. Extensive inclusion/exclusion criteria have been chosen in this study to restrict the target population to those thought to be best served by this EV ICD system and mitigate the risk of selection bias. Enrollment can be a stand-alone visit or can occur on the same day as the baseline visit. After that subjects will undergo implant of the EV ICD system, with required defibrillation, sensing, impedance and pacing testing. Subjects will then return for follow-up visits at 2 Weeks, 3 Months, 6 Months, and every 6 months thereafter. Subject disposition will be presented using a flow diagram where completed visits, missed visits, and attrition due to exit and death will be indicated.

7.1.2 Clinical Investigation Plan (CIP) Deviations

A study deviation is an event within a study that did not occur according to the CIP or the Clinical Trial Agreement. Study deviations will result in corresponding Study Deviation eCRFs being completed. These deviations will be summarized with descriptive statistics including, for each type of deviation, how many occurrences there were in the study, and the number of subjects experiencing each type of deviation. Inclusion/exclusion violations will not result in subjects being excluded from analysis of objectives. Of particular importance will be required testing not completed at implant or follow-up. If it is discovered there were subjects not meeting the inclusion/exclusion criteria who underwent an implant attempt and possibly defibrillation testing, additional analyses may be performed with these subjects excluded.

7.1.3 Analysis Sets

All subjects with an implant attempt of the investigational product will be included in the primary analysis for the primary safety objective. All subjects who complete the defibrillation protocol will be included in the primary analysis for the primary efficacy objective. Results from the primary analyses will determine if the primary safety and efficacy objectives are met. In addition, sensitivity analyses may be

considered to assess the robustness of the results when there is missing data. For example, patients who begin the defibrillation testing at implant but do not complete it may be included in the sensitivity analysis for the primary efficacy objective.

7.2 General Methodology

Data analysis will be performed by Medtronic statisticians or designees.

The cohort will include all enrolled subjects who undergo the study procedures unless the subject does not complete the required testing, and there are no pre-specified subgroups for assessment. For endpoints involving only measurements collected at follow-up visits, only subjects who complete those visits will be included in the analysis of those endpoints.

7.3 Poolability

This study plans to enroll up to 400 subjects at up to 60 sites worldwide. Poolability analysis may be performed to compare the results between different geographic regions such as ANZ, EMEA, Japan, Hong Kong, and United States/Canada. Consistency between the regions for the primary safety endpoint will be evaluated using a log-rank test, that for the primary efficacy endpoint will be evaluated using Fisher's exact test. If these tests indicate that the homogeneity of study results across regions may be a concern, further analyses will be performed to determine potential explanations for the possible heterogeneity.

7.4 Handling of Missing, Unused, and Spurious Data and Dropouts

All available data will be included in the data listings and tabulations.

Only subjects who complete the defibrillation protocol at implant will be included in the primary analysis that determines if the primary efficacy objective is met. Subjects who do begin the defibrillation testing at implant but do not complete it may be included in a sensitivity analysis. Specifically, a tipping point analysis may be performed based on all subjects that have begun the defibrillation testing at implant to determine the robustness of this analysis to missing data.

With regard to the primary safety objective, subjects who exit the study prior to experiencing a major system or procedure-related complication will be censored at the date of their exit (in the case of the subject being lost to follow-up or death of unknown classification, the subject will be censored at the date of last contact with the subject) in the calculation of any Kaplan-Meier freedom from complication rates. In the situation where the attrition rate is much higher than expected or there appears to be a systematic reason for attrition, the assumption of noninformative censoring may no longer be valid and a sensitivity analysis may be considered.

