
Not Related
	
Relationship to the device or procedures can be excluded when:
 
 • The event is not a known side effect of the product category the device belongs to or of similar devices and procedures; • The event has no temporal relationship with the use of the device or the procedures; • The serious event does not follow a known response pattern to the medical device (if the response pattern is previously known) and is biologically implausible; • The discontinuation of medical device application or the reduction of the level of activation/exposure – when clinically feasible – and reintroduction of its use (or increase of the level of activation/exposure) do not impact the serious event; • The event involves a body-site or an organ not expected to be affected by the device or procedure; • The serious event can be attributed to another cause (e.g., an underlying or concurrent illness/clinical condition, an effect of another device, drug, treatment, or other risk factors); • The event does not depend on a false result given by the device used for diagnosis (when applicable); • Harm to the subject are not clearly due to use error; • In order to establish the non-relatedness, not all the criteria listed above might be met at the same time, depending on the type of device/procedures and the event.

EV ICD Pivotal Study Clinical Investigation Plan

MDT16028

Version 1.0, 02-JUL-2019

Page 89 of 165

Medtronic

Unlikely	The relationship with the use of the device seems not relevant and/or the event can be reasonably explained by another cause, but additional information may be obtained.
Possible	The relationship with the use of the investigational device is weak but cannot be ruled out completely. Alternative causes are also possible (e.g., an underlying or concurrent illness/ clinical condition or/and an effect of another device, drug or treatment). Cases where relatedness cannot be assessed or no information has been obtained should also be classified as possible.
Probable	The relationship with the use of the investigational device seems relevant and/or the event cannot reasonably be explained by another cause, but additional information may be obtained.

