Complication	
An adverse event that includes the following is considered a complication:
 
 • Results in death, • Involves any termination of significant device function (i.e., defibrillation therapy), or • Requires an invasive intervention 
Non-invasive (21 CFR 812.3(k)): when applied to a diagnostic device or procedure, means one that does not by design or intention: Penetrate or pierce the skin or mucous membranes of the body, the ocular cavity, or the urethra, or enter the ear beyond the external auditory canal, the nose beyond the nares, the mouth beyond the pharynx, the anal canal beyond the rectum, or the vagina beyond the cervical os
 
For purposes of this part, blood sampling that involves simple venipuncture is considered non-invasive, and the use of surplus samples of body fluids or tissues that are left over from samples taken for non-investigational purposes is also considered non-invasive.
 
Note: Only system or procedure related AEs will be classified as complication (major, minor) or observation.

Major complication	
A system or procedure-related complication which results in:
 
 • Death • Permanent loss of defibrillation function due to mechanical or electrical dysfunction of the device • Hospitalization • Prolongation of an existing hospitalization by at least 48 hours • System revision (reposition, replacement, explant) 
Note: Only system or procedure related AEs will be classified as complication (major, minor) or observation.

Minor complication	
Any complication that is not a major complication (e.g., event classified as a complication solely based on intravenous drug administration).
 
Note: Only system or procedure related AEs will be classified as complication (major, minor) or observation.

Observation	
Any adverse event that is not a complication.
 
Note: Only system or procedure related AEs will be classified as complication (major, minor) or observation.

EV ICD Pivotal Study Clinical Investigation Plan

MDT16028

Version 1.0, 02-JUL-2019

Page 92 of 165

Timing																	
Pre-Implant Procedure	Occurs after the IC has been signed but before the skin incision during the EV ICD implant procedure.																
During Implant Procedure	Occurs during the EV ICD implant procedure, after skin incision and prior to completion of skin closure.																

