10.7. Death Classification and Reporting

Sufficient information will be required in order to properly classify the subject’s death. The Investigator shall classify each subject death per the following definitions:

Cardiac Death: A death directly related to the electrical or mechanical dysfunction of the heart.

- Sudden Cardiac Death (SCD): Natural death due to cardiac causes, indicated by abrupt loss of consciousness within one hour of the onset of acute symptoms; preexisting heart disease may have been known to be present, but the time and mode of death are unexpected. If time of onset cannot be determined, SCD will alternatively be defined as any unexpected cardiac death occurring out of the hospital or in the emergency room as dead on arrival.
- Non-sudden Cardiac Death: All cardiac deaths that are not classified as sudden deaths, including all cardiac deaths of hospitalized subjects on inotropic support.

Non-cardiac Death: A death not classified as a cardiac death.

Unknown Cardiac Classification: Unknown death classification is intended for use only when there is insufficient or inadequate information to classify the death.

The Clinical Events Committee will also review all deaths and provide an adjudication of the death classification. See section 11.1 for handling events where the adjudication of the investigator and the CEC differ.

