11.1. Clinical Events Committee

The study will utilize an independent Clinical Events Committee (CEC). At regular intervals, an independent CEC will review events and adjudicate at a minimum all system and procedure-related events. Additionally, the CEC will provide an adjudication of the death classification for all reported deaths.

The CEC will consist of a minimum of three (3) non-Medtronic-employed physicians whose site is not participating in the study, including a CEC chairperson.

Medtronic personnel may facilitate and participate in CEC meetings but will be non-voting members.

For AEs and deaths reviewed by the CEC, Medtronic will provide the CEC with the Investigator's description and supportive documentation (when available). The CEC is responsible for reviewing the Investigator's description and supportive documentation (when available), reviewing applicable definitions, and determining final classifications for all adjudication parameters. For AEs, classification includes system/procedure relatedness and complication (major, minor) or observation. Additionally, the CEC will provide an adjudication for all reported deaths, including system/procedure relatedness and cardiac relatedness.

If the CEC disagrees with the investigator's classification of the event, the difference will be provided to the investigator. If the investigator agrees with the CEC's adjudication, the eCRF documenting the AE will be updated accordingly.

If the investigator does not agree with the CEC's adjudication classification, both determinations will be provided within the final report; however, the CEC's adjudication will be used for data analysis. The disagreement will also be included in reporting to ethics committees and regulatory authorities, if required.

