7.9.1.2 Performance Requirements and Endpoint Definition

Performance requirements for this objective define both the endpoint and the OPC. The endpoint is defined as a subject's first occurrence of a major complication related to the EV ICD System and/or procedure as determined by the independent Clinical Event Committee (CEC) that occurs on or prior to 6 months (182 days) post-implant.

For an adverse event to meet the endpoint, the event must have occurred within 182 days (inclusive) of the EV ICD System implant attempt and be adjudicated by the CEC as being a major complication related (causal relationship) to the EV ICD System and/or procedure. Major complications are those complications resulting in:

- Death
- Permanent loss of defibrillation function due to mechanical or electrical dysfunction of the device
- Hospitalization (see CIP Table 12 or Hospitalization definition)
- Prolongation of an existing hospitalization by at least 48 hours
- System revision (reposition, replacement, explant)

[figure not shown]
The pre-specified OPC for the major complication free rate at 6 months is 0.79, meaning the lower confidence bound of two-sided 95% confidence interval for the freedom from EV ICD major complication incidence rate must exceed 0.79.

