7.9.1.4 Analysis Methods

Results will be summarized in aggregate using descriptive statistics. The total number of major complications experienced by subjects for whom an implant is attempted will be summarized. The primary analysis for primary safety endpoint will be based on the endpoint definition described in section 7.9.1.2. Subjects not experiencing an event will be censored at their last point of contact. The 182-day freedom from major complication rate will be generated using the Kaplan-Meier method, along with a two-sided 95% confidence band based on a log-log transformation. If the lower bound is at least 0.79 (79%), the objective will be considered met.

If any adverse events that occurred within 182 days (inclusive) of the EV ICD System implant attempt were adjudicated by the CEC as being major complications and the relatedness to the EV ICD System and/or procedure was determined by the CEC as “probable”, a sensitivity analysis will be conducted with such adverse events included as having met the primary safety endpoint. An additional sensitivity analysis may be performed including major complications with a system or procedure-relatedness classification of “possible”, should there be any such major complications.

Comparison against the pre-specified OPC with the full cohort of subjects that have undergone an implant attempt is considered a confirmatory analysis of this objective.

Noninformative censoring is assumed in the primary analysis. In the situation where the attrition rate is higher than expected or there appears to be a systematic reason for attrition that may bias the results, the assumption of noninformative censoring may no longer hold and a sensitivity analysis such as a tipping point analysis may be considered.

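### Does censoring a death of unknown classification at last contact (SAP 7.4) hide device-related deaths from the primary safety endpoint?

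*SAP*

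**What the plan says.** SAP 7.4 deals with subjects who leave the study before any endpoint event. They are censored at exit, except that for loss to follow-up or a "death of unknown classification, the subject will be censored at the date of last contact with the subject".

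CIP 10.7 defines the classes of death by cardiac cause and restricts the last one: "Unknown death classification is intended for use only when there is insufficient or inadequate information to classify the death". When time of onset cannot be determined, the same section places in sudden cardiac death "any unexpected cardiac death occurring out of the hospital or in the emergency room as dead on arrival".

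Relatedness is a separate judgement. CIP 11.1 states that "the CEC will provide an adjudication for all reported deaths, including system/procedure relatedness and cardiac relatedness". CIP Table 12 gives the default grade when evidence is lacking: "Cases where relatedness cannot be assessed or no information has been obtained should also be classified as possible".

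SAP 7.9.1.2 counts a major complication as a primary event only if the CEC finds a causal relationship to the system or procedure. For major complications graded *probable*, SAP 7.9.1.4 commits itself: "a sensitivity analysis will be conducted with such adverse events included as having met the primary safety endpoint". For those graded *possible*, the same section names a further sensitivity analysis but makes it optional. A tipping-point analysis is also optional, for attrition that is higher than expected or looks systematic.

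SAP 7.9.8.4 commits to listing individual adverse events with outcome, relatedness and seriousness. SAP 7.10 commits to listing each death with the investigator's and the CEC's classification.

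**The concern.** Suppose a subject dies at home at month four and little is known. The class may be unknown, and relatedness that cannot be assessed defaults to *possible*. The death is then not a primary event, and the subject is censored at last contact. If the device or the procedure was in fact responsible, the complication-free rate is too high. No committed Kaplan-Meier analysis would show by how much: the *possible* analysis is optional, and one or two deaths would not look like unusual attrition.

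In a defibrillator trial an unexplained death may be a failure of therapy, and the primary analysis alone decides the objective (SAP 7.1.3). A reader could fairly ask for a supporting run fixed before the data are seen.

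**Working it through.** **Which rule decides whether a death counts.** The documents treat a death within 182 days by its CEC relatedness grade:

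| CEC grade | Primary analysis | Supporting analysis | Listed |
|---|---|---|---|
| causal | event | – | yes |
| probable | censored | committed | yes |
| possible | censored | named, optional | yes |
| unlikely or not related | censored | none | yes |

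Cardiac class appears nowhere in this table. Remove the unknown-class wording from SAP 7.4 and a death graded *possible* is still censored, because SAP 7.9.1.4 censors every subject without an event at last contact. A sudden cardiac death graded *possible* is treated in the same way. The residual gap is therefore the optional status of one sensitivity analysis.

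**The plan's own figure.** Inputs from SAP 6.1: 292 subjects; Weibull event times with 90% free at 1 month and 86% at 6 months; Weibull attrition of 9% at 1 month and 16% at 1 year; limit 79%; stated power 90%. Simulating this design with the log-scale bound used for sizing gives 89.4% to 89.8%, so the stated power reproduces. The log-log bound of SAP 7.9.1.4 gives 83.4% to 84.0%. That difference is a separate matter; the log-log bound is used below.

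**Expected number of such deaths.** The documents give none, so this is an assumption. CIP Table 29 reports 1 death of unknown cause among 314 subcutaneous-ICD subjects followed for 180 days: 1/314 × 292 = 0.93. The exact 95% interval on 1/314, scaled to 292, is 0.02 to 5.1. With a Poisson mean of 0.93, P(at least 1) = 0.61 and P(at least 3) = 0.07.

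**Distance to the limit, ignoring censoring.** With e events in n = 292, S = 1 − e/n, g = e/[n(n − e)], and the lower bound is S^exp(1.96·√g/|ln S|).
- e = 47: S = 0.8390, bound 0.7916, pass.
- e = 48: S = 0.8356, bound 0.7879, fail.
- At 86%, expected e = 0.14 × 292 ≈ 41, so about 48 − 41 = 7 added events would reverse the result.

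**With attrition, by simulation** (8,000 trials per true rate; k deaths spread evenly over days 1 to 182; last contact assumed 15 days before death; each counted as an event in the supporting run). The 6-month estimate falls on average by 0.37 points for one death, 0.75 for two and 1.12 for three. Share of trials passing the primary test that fail the supporting run:

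| True 6-month rate | k = 1 | k = 2 | k = 3 |
|---|---|---|---|
| 85% | 8.1% | 17.5% | 27.1% |
| 86% | 5.4% | 11.9% | 19.3% |
| 88% | 1.1% | 2.4% | 4.9% |
| 90% | 0.1% | 0.2% | 0.4% |

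A repeat with 4,000 trials per rate gave 8.8%, 5.4% and 1.1% for k = 1 at 85%, 86% and 88%.

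Weighting by the Poisson probabilities of 1, 2 and 3 or more deaths (0.367, 0.171, 0.068; 3 or more treated as 3):
- 86%: 0.367 × 5.4 + 0.171 × 11.9 + 0.068 × 19.3 ≈ 5.3%
- 88%: 0.367 × 1.1 + 0.171 × 2.4 + 0.068 × 4.9 ≈ 1.1%
- 90%: 0.367 × 0.1 + 0.171 × 0.2 + 0.068 × 0.4 ≈ 0.1%

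Median number of deaths needed to tip a passing result, by observed rate: 1 at 84%, 2 at 84.5%, 3 at 85%, 6 at 86%, 11 at 88%, 16 at 90%. The lowest passing estimate is about 83.9%.

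**The case for a change.** The strongest case for a change is that an analysis chosen after the data are seen carries less weight than one fixed beforehand, and that fixing it would cost a sentence and one Kaplan-Meier run on data already collected. It is also true that *possible* is the default grade when information is lacking, and that no committed Kaplan-Meier run covers it. Both points stand, but as a matter of degree. The SAP already names the analysis, so it would not be invented after the fact, and the events it needs will be visible in committed listings.

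A further argument is that an unassessable death might miss even the optional analysis, because CIP Table 12 says "Only system or procedure related AEs will be classified as complication (major, minor) or observation". This is weak. SAP 7.9.1.4 expressly allows for major complications graded *possible*, so the SAP treats that grade as compatible with the label.

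A special analysis restricted to unknown-class deaths would also miss its own purpose. The unexpected out-of-hospital cardiac death, the likeliest sign of therapy failure, can be classed as sudden cardiac and would be left out. Counting such deaths in the primary analysis would be a different matter: at the planning rate, log-log power would fall from about 0.84 to 0.80 with one death and 0.70 with three. Nothing here calls for that.

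**Conclusion.** No change is needed. SAP 7.4 sets a censoring date and does not decide which deaths count. CEC relatedness grading does that, for every death and whatever its cardiac class. The remaining looseness is that the *possible* sensitivity analysis is optional, a gap that an analyst who sees such a death can fill from the SAP's own text. CIP 10.6 requires the date of death to be collected, the committed listings show relatedness and death class, and SAP section 3 does not limit analyses to those planned.

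The effect is about 0.4 points on the 6-month estimate per death, with the primary decision unchanged. One death alters the reading only near an observed 84%, and three only at about 85% or lower. The planning rate is 86%, and the historical 6-month rates in SAP Table 1 run from 85.3% to 93.8%.

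These figures assume about one such death per 292 subjects, taken from a single event in another device's trial, where unknown cause is not quite the same as unknown cardiac class. They also assume a 15-day gap from last contact to death, and they count every such death as an event, which overstates the effect if some were unrelated.
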